4.6 Expected Duration of Participation

Once enrolled, each participant is expected to complete approximately 2 weeks (14 days \pm 3 days) on the study.

4.7 Sites

The study site(s) will be located in sub-Saharan Africa and will be selected by the MTN Executive Committee. The site(s) will be selected based on participation in VOICE as well as capacity.

5 STUDY POPULATION

5.1 Selection of the Study Population and Recruitment

The inclusion and exclusion criteria in Sections 5.2 and 5.3 will be utilized to ensure the appropriate selection of study participants.

5.2 Inclusion Criteria

Potential participants must meet all of the following criteria to be eligible for inclusion in the study:

- 1) Age 18 – 45 years, inclusive at screening
- 2) Presented and screened out of the VOICE trial
- 3) Able and willing to perform the study procedures

- 4) Able and willing to provide informed consent for study participation
- 5) Has tested HIV-negative within 90 days of enrollment, per VOICE screening laboratory results
- 6) Is currently not pregnant, per VOICE laboratory results or self-report
- 7) Willing and able to provide locator information to the research team

5.3 Exclusion Criteria

Potential participants who meet the following criteria will be excluded from the study:

- 1) Has any condition that, in the opinion of the IoR/designee, would preclude informed consent, make study participation unsafe, complicate interpretation of study outcome data, or otherwise interfere with achieving the study objectives.
- 2) Screened out of VOICE for any clinical condition, that in the opinion of the IoR, may require monitoring or care beyond the scope of this pilot study.

6 STUDY PRODUCT

The Wisebag pilot study will not involve the administration of any study product. In lieu of study products, participants will be provided with peel-off stickers that will be dispensed in the Wisebag.

6.1 Supply and Dispensation of Wisebag

All three types of Wisebag containers will be manufactured and supplied by Wisepill Technologies. Wisebags and study stickers will be dispensed only to enrolled participants, following Informed Consent and randomization. Each participant will receive one type of Wisebag, based on the randomization scheme. Dispensing will take place on the day of enrollment.

7 STUDY PROCEDURES

Additional information on visit-specific study procedures are presented in this section. Detailed instructions to guide and standardize procedures across sites are provided in the MTN-003-P01 SSP Manual located at <http://www.mtnstopshiv.org>.

7.1 Screening and Enrollment

The Screening and Enrollment Visit for the Wisebag pilot should take place within approximately 4 weeks of the last VOICE Screening Visit; however participants may be enrolled up to 90 days after the date of the last VOICE Screening Visit. Screening for all data collection activities will include oral or written confirmation that participants meet the inclusion and exclusion criteria. Study staff will create checklists to ensure this is consistently documented.

Table 1: Screening and Enrollment

Screening and Enrollment	
Component	Procedures
Administrative and Regulatory	
 • Obtain informed consent • Confirm eligibility • Obtain locator information • Randomization • Schedule next (exit) visit • Provide counseling regarding protocol adherence • Provide reimbursement for study visit
Behavioral	
 • Conduct demographic and brief behavioral assessment • Dispense (2) weekly diary cards as well as the Wisebag along with instructions on use. • Practice opening/closing the bag and placing a study sticker on their diary card

7.2 Exit Visit: End of Week 2

Visit window at target exit visit date: The target visit exit date will be 2 weeks (14 days) from the enrolment date, with an allowable visit window of plus or minus 3 days. Participants who present late for their exit visit (Day 18 or later) will complete study procedures, as long as the study is still in the accrual phase. Otherwise, the participant will be classified as lost to follow up if they missed the exit visit window and there were 3 unsuccessful contact attempts.

Table 2: Exit Visit: End of Week 2

Week 3	
Component	Procedures
Administrative and Regulatory	
 • Collect Wisebag from participant. • Download data from the 2 week period from all “active” Wisebags • Provide reimbursement for study visit • Debrief on the full purpose of the research
Behavioral	
 • Conduct behavioral and acceptability assessment • Collect and review diary card • Semi-structured brief qualitative interview • Perceived Wisebag product

7.3 Interim Visits:

Interim visits may be performed at any time from enrollment to Day 10 for the reasons listed below. Interim visits after Day 10 (and before Day 14) will be in the Exit visit window and an Exit visit will be conducted in lieu of an interim visit. All interim contacts and visits will be documented in participants' study records and on applicable CRFs.

- For administrative reasons, e.g., a participant may have questions for study staff, or may need to re-schedule a follow-up visit.

- For Wisebag use or data collection related reasons, e.g., a participant may need additional stickers, a new diary card or a replacement Wisebag because of malfunction (e.g. the zipper is broken), loss or theft.
- In response to social harm or safety concerns. Although this is not expected to happen, given the minimal risk associated with this study, participants will be told to come to the study in case such an unexpected event happens. In such occasion, study staff will assess the reported event clinically and provide or refer the participant to appropriate medical or psychological care as required.
- For other reasons at participant request.

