- Study Duration:** Approximately 10 weeks total: accrual will require approximately 8 weeks. Additionally, the follow-up period will take approximately 2 weeks. Each participant will have 2 visits, 2 weeks apart.
- Study Product:** N/A
- Study Regimen:** Study stickers will be stored in the Wisebag and used in lieu of actual products for this pilot. In all three groups, participants will be asked to open their assigned Wisebag daily, peel off a sticker, and place it on a study-provided diary card.

Primary Objectives:

- To compare the on-site technical performance of the “offline” and “online” functionalities of Wisebag
- To assess the success of attempted blinding of the “dummy” vs. active (“online” or “offline”) Wisebag
- To measure the concordance between Wisebag opening-event data (both “online” and “offline”) and self-reported data.

- To explore the feasibility and acceptability of Wisebag use by participants

Primary Endpoints:

- **Technical Performance**
 - Staff-reported and participant-reported technical and user-related problems with device and bag; diary card and signal data from device (“heart beat” and participant-initiated opening-events)
- **Ability to Identify Randomization Arm**
 - Participants’ self-evaluation of their arm assignment and their ability to detect (at study exit) whether a bag is an active or non-active bag
- **Concordance with Self-Report**
 - Opening-event data (downloaded from device at the clinic or sent wireless to server) compared with self-reported diary card and questionnaire data
- **Feasibility and Acceptability**
 - Participant attitudes and experiences with Wisebag assessed through questionnaire and open-ended interview data at study exit

Secondary Objective:

- To assess the appropriateness of educational materials/instruction sheets for Wisebag use

Secondary Endpoint:

- Appropriateness of educational materials will be assessed through questionnaire and open-ended interview data at study exit.

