2.4 Wisepill/Wisebag Technology

Wisebag™ (Wisepill Technologies Adherence Management Solutions, South Africa) is a portable, lunch-bag size container, which can contain approximately 30 individually wrapped gel applicators or more, closes with a zipper, and has a self-contained battery-operated electronic device that includes a chip which provides an electronic signal each time an opening event occurs, and counts and records any opening events, as well as a daily control signal ('heart beat') to signify proper battery functioning. Wisebag event monitoring system can be set-up such that all data are stored in the device until the information is downloaded at the clinic at follow-up visits (offline modality) or, each time an event occurs, a signal is sent to the central management system in real-time through a wireless system (online modality). Through this latter modality, it is possible to monitor adherence on an ongoing, 'real time' basis. The real time data capture and monitoring, although more expensive, allows up to the minute insight on patterns of use and non-use as well as the ability, where appropriate, to follow up with participants when non-adherent.

In recent HIV treatment studies, as described above, the Wisepill, a similar device using wireless technology to monitor tablet use, has allowed assessment of tablet-taking opening events in real time, and in combination with cell-phone reminders.^[15] In another recent study, Wisebag was piloted among 10 participants in the CAPRISA 004 trial, and this was the first application of such a technology to the microbicide context^[11]. Another pilot study currently being conducted in Uganda among 50 caretaker/infant pairs is using Wisebag for pediatric liquid HIV treatment in Uganda ([name], personal communication).

Like Wisepill and MEMS caps, the Wisebag electronic device monitors each opening event of the bag, and provides a date and time stamp of when these occurred. This non-invasive indirect objective approach to monitor adherence, has thus been adapted to monitor gel applicator use.

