4 STUDY DESIGN

4.1 Identification of Study Design

MTN-003-P01 is a three-arm, randomized, placebo-controlled, double-blinded pilot study of Wisebag for monitoring daily product use. The study is double-blinded with respect to participants and investigators, (but not for pharmacy and information technology (IT) staff who will manage the download of the electronic data and the battery charging of Wisebag devices). Approximately 50 participants will be randomized to the 3 study arms in a 1:2:2 ratio. The 3 groups will be “dummy” Wisebag (n~10) “Online device” Wisebag (n~20), or “Offline device” Wisebag (n~20).

There will be two study visits: an enrollment visit and one follow-up/exit visit, two weeks after enrollment. During study participation, participants will be asked to open their assigned Wisebag at approximately the same specified time daily, to peel off one sticker from a set of study stickers inside the bag, and place the sticker on the appropriate day of the week on a study provided diary card. After two weeks of daily openings, participants will be asked to return to the study clinic for an exit visit with their Wisebag and diary card.

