4.4 Time to Complete Accrual

The accrual period is targeted over approximately 8 weeks.

4.5 Study Groups:

The three study groups are as follows:

- "Dummy" or placebo Wisebag group: this group will receive a Wisebag which looks and feels identical to an active-device Wisebag, but has no battery or electronic recording system inside the device.
- "Online device" Wisebag: Active-device Wisebag with wireless component and SIM card for sending in real-time all opening events to a central server, in addition to a battery.
- "Offline device" Wisebag: Active-device Wisebag without the wireless component and the SIM card, and with battery and electronic recording system to store all opening events, which are then downloaded to a server at the clinic site.

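### Section 7.2 allows a late exit visit only while accrual is open, so about the last third of women enrolled have no late-exit allowance and a late but reachable woman has no stated disposition

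*Protocol*

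**What the plan says.** Section 7.2 sets the exit visit at 14 days from enrolment, "with an allowable visit window of plus or minus 3 days", which is Day 11 to Day 17. A woman presenting on Day 18 or later "will complete study procedures, as long as the study is still in the accrual phase". The next sentence covers the alternative: "the participant will be classified as lost to follow up if they missed the exit visit window and there were 3 unsuccessful contact attempts".

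On timing, Section 4.4 states: "The accrual period is targeted over approximately 8 weeks". The Protocol Summary adds two weeks of follow-up: "Approximately 10 weeks total: accrual will require approximately 8 weeks". On size, Section 4.1 states: "Approximately 50 participants will be randomized to the 3 study arms in a 1:2:2 ratio"; Section 10.4 gives 10 dummy, 20 online and 20 offline.

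Table 2 in Section 7.2 places the device download, diary collection, behavioral and acceptability assessment, interview, perceived-bag question and debriefing at the exit visit. Section 2.4 describes the offline data path: "all data are stored in the device until the information is downloaded at the clinic at follow-up visits (offline modality"). The same section says that online events are sent in real time and give daily data even when a bag is not brought back.

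**The concern.** The condition on late visits has no link to the participant, her bag or the quality of her data. Of two women who are equally late, the one enrolled early in accrual completes the exit procedures under a stated rule and the one enrolled near the end does not.

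All four primary endpoints in Section 4.2 draw on exit data, so a missed exit touches each of them. For an offline bag, the exit download also retrieves the only copy of the opening events. Online versus offline performance is the first primary objective, and with 20 women per active arm each lost record is 1/20 = 5% of an arm.

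The two sentences in Section 7.2 also do not join up. The second needs both a missed window and three failed contacts. A woman who walks in on Day 18 after accrual has closed has plainly been reached, so she fits neither sentence. Section 7.3 does not cover her either, because interim visits stop at Day 10.

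**Working it through.** The protocol states no late-attendance figure to reproduce. Its planning figures agree with each other: 8 + 2 = 10 weeks, and 50 split 1:2:2 gives 10, 20 and 20.

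**Inputs from the protocol.** Accrual of about 8 weeks = 56 days (Section 4.4); last in-window day 17 and first late day 18 (Section 7.2); 50 women, 20 of them offline (Section 10.4).

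**Assumptions.** Uniform enrolment over the accrual period; late-attendance rate of 5% to 30%. The protocol gives neither.

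**Step 1: share with no late allowance.** A woman enrolled on accrual day t reaches Day 18 on day t + 18. This falls after accrual closes when t > 56 − 18 = 38.

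- Share: 18/56 = 32.1%.
- All women: 50 × 18/56 = 16.1.
- Offline: 20 × 18/56 = 6.4.
- Counting from Day 17 instead: 17/56 = 30.4%, or 15.2 women.
- If accrual took 6 weeks: 18/42 = 42.9%. If it took 10 weeks: 18/70 = 25.7%.

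**Step 2: expected number affected.** Number × 18/56 × late rate.

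| Late rate (assumed) | Of 50 women | Of 20 offline |
|---|---|---|
| 5% | 0.8 (1.6%) | 0.3 |
| 10% | 1.6 (3.2%) | 0.6 |
| 20% | 3.2 (6.4%) | 1.3 |
| 30% | 4.8 (9.6%) | 1.9 |

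**Step 3: later presentation.** Step 2 treats each late woman as presenting on Day 18. For one presenting on Day d the share is d/56, so women enrolled before the last 18 days can also be caught. If late visits were spread evenly over Days 18 to 25, the mean share would be 21.5/56 = 38.4%, and 50 × 0.384 × (0.05 to 0.30) gives about 1.0 to 5.8 women. The order of magnitude does not change.

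**Step 4: which data are at risk in which arm.**

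- Diary, questionnaire, interview and blinding answers are collected at the exit visit in all three arms, so the risk is the same in each.
- Signal data do not exist for dummy bags. Online events are already on the server. Offline events are on the device until the clinic download.
- Concordance (Section 10.5.2) needs the diary as well as the signal, so an online woman with no exit visit drops out of that endpoint too. The arm difference is therefore confined to the signal part of technical performance.

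**The case against.** The strongest case against acting is that the numbers are small. This is an exploratory pilot that Section 2.6.1 says is not designed to test a hypothesis, and one or two missing exits would hardly change its descriptive conclusions. Every study must stop taking late visits at some point, and the rule applies alike to all arms. The vulnerability of offline data is a property of the device and would exist under any cut-off. Section 7 leaves detailed procedures to a manual that is not shown. These points stand as limits on size. They do not remove the defect: the cut-off is tied to an event unrelated to follow-up, although the site must stay open for the last enrollee's window anyway, and Section 13.3 says that implementation is directed by the protocol.

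A reader might infer three stronger things that the document does not support:

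- **That a third of women lose their exit data.** The 32% is the share without a late allowance. Women who attend on Days 11 to 17 are unaffected whenever they enrolled.
- **That late women are turned away or their bags left unread.** Refusal is implied by the accrual condition but nowhere stated. Loss of the offline record is a risk, not a stated result.
- **That all missing exit data would differ by arm.** Only signal data would.

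**Conclusion.** The concern holds in a limited form. Section 7.2 makes completion of a late exit depend on whether accrual is open, and gives no disposition to a woman who is late after accrual closes but reachable. Under uniform 8-week accrual, about 16 of 50 women, including about 6 of 20 offline, have no late allowance. The expected number affected is about 0.8 to 4.8 of 50, and about 0.3 to 1.9 of 20 offline, at an assumed late rate of 5% to 30%. That is a modest but avoidable loss of primary-endpoint data, and for offline bags it could include the sole copy of the signal record. The correction is worth making because it is nearly free, not because the expected loss is large.

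**What to change.** In Section 7.2:

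1. Delete the clause that makes late completion depend on open accrual.
2. State one close-out date, no earlier than the last enrollee's Day 17. Until then, accept late exits and download returned bags from every participant.
3. Classify as lost to follow-up only women not seen by that date after three failed contact attempts. This closes the gap between the two sentences.
4. Analyse the same 14-day period for everyone, so that late exits do not lengthen exposure. Table 2 already refers to a two-week download and Table 1 to two weekly diary cards, so this mainly confirms what is there.

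Cost: wording only, with no added participants or procedures. Close-out at the last enrollee's Day 17 falls at 56 + 17 = 73 days, when the site is open anyway, so it needs little or no extra time. It shrinks the inequality without removing it: a woman enrolled on accrual day t then has 56 − t days beyond her own Day 17, and the last enrollee has none. Closing one or two weeks later would give every woman at least 7 or 14 days, at the price of that extra time.

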7.4 Behavioral Evaluations

Using electronic monitoring event opening signals, diary cards and/or interview-administered questionnaires, the following behaviors will be assessed:

- Adherence to daily opening events of the Wisebag
- Technical problems and user related issues with Wisebag, including ease/difficulty of use, storage, curiosity events (by self or others), disclosure/secretcy, sharing or theft of Wisebag or stickers, etc.
- Use of Wisebag for non-study purposes (e.g. to store food, personal items etc.)
- Acceptability of use of Wisebag

To ensure that study participants understand how to use the Wisebag and stickers, and how to complete the daily diary card on their own, study staff will guide each participant through a practice session at the enrolment visit.

7.5 Blinding Evaluations

At the exit visit, women will be asked by an interviewer if they believe they were assigned to a dummy or an active device Wisebag. Following completion of the behavioral assessments, each participant will be shown two demonstration Wisebags, one dummy and one active, and will ask to indicate to the interviewer which one she believes is the active and which one she believes is the dummy. Data will be recorded on an appropriate CRF.

8 ASSESSMENT OF SAFETY

The Wisebag pilot study will involve minimum risk: it does not involve ingesting or topically applying a study product and does not involve any clinical, laboratory or other procedures associated with risk to participants. Therefore, few safety concerns are expected as a result of study participation. The study site IoR is responsible for continuous monitoring of all study participants and for alerting the protocol team if unexpected concerns arise. Study sites will have written procedures for ensuring prompt reporting to the Institutional Review Board (IRB)/Ethics Committees (EC), of any unanticipated problem involving risks to subjects or others. No safety events will be captured in the study database.

8.1 Safety Monitoring

Site IoRs are responsible for continuous close safety monitoring of all study participants, and for alerting the Protocol Team if unexpected concerns arise. Since the safety risks are minimal in

this pilot study, if any such unexpected concerns arise, the team will notify an appropriate on-site staff member (Site Clinician, Counselor, Nurse) affiliated with the CRS for follow-up.

The Manual for Expedited Reporting of Adverse Events to Division of AIDS (DAIDS) will not be used for this study for the following reasons: 1) this study does not involve a study drug and is non-invasive; 2) adverse events are not primary or secondary objectives of the study. Untoward clinical or medical occurrences reported by study participants to have been experienced during study participation will be recorded in participant file notes.

8.2 Social Harms Reporting

Social harms are considered to be non-clinical adverse consequences that may occur as a result of study participation. For example, although the study site will make every effort to protect participant privacy and confidentiality, it is possible that participants' involvement in the study could become known to others and this may cause physical, emotional or psychological problems for the participants. Social harms that are judged by the IoR/designee to be serious or unexpected will be reported to the DAIDS MO and responsible site IRBs according to their individual requirements.

9 CLINICAL MANAGEMENT

There are no additional clinical management considerations for participants enrolled in the Wisebag pilot. Participants who express concerns with social, psychological or clinical issues will be referred for appropriate care to services available at the CRS, or at nearby partnering facilities.

10 ANALYTICAL CONSIDERATIONS

10.1 Overview and Summary of Design

The Wisebag pilot study is an exploratory study using quantitative and qualitative data collection methods. It involves electronic event monitoring signal data, sent over wireless phone or directly downloaded from the Wisebag devices onto a server, self-collected diary data, and interviewer collected survey data, and qualitative open-ended textual data.

10.2 Study Endpoints

The main outcomes of interest in the Wisebag pilot will be 1) technical and user-related performance of the Wisebag in the online modality versus the offline modality 2) success of attempted blinding, 3) signal accuracy of the events monitoring in the online modality versus the offline modality as compared to the diaries provided by participants, and 4) participant attitudes and experiences with Wisebag.

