2.2 The MTN-003 (VOICE) Study

MTN-003, the Vaginal and Oral Interventions to Control the Epidemic (VOICE) Study is designed to assess the safety and efficacy of daily dose oral and vaginal formulations of tenofovir and oral emtricitabine/tenofovir disoproxil fumarate (FTC/TDF) in preventing HIV acquisition. The VOICE study is a Phase 2B, five-arm, multi-site, randomized, placebo-controlled trial that is double-blinded within each mode of administration, but open-label with respect to the randomly assigned mode of administration (vaginal or oral). Approximately 5000 participants will be randomized to the five study arms in a 1:1:1:1:1 ratio. The VOICE study is being implemented in sub-Saharan Africa.

A secondary objective of the VOICE study includes the evaluation of adherence to daily regimens of vaginal gel (tenofovir 1% gel and placebo) vs. oral tablets (TDF, FTC/TDF, and placebos) used to prevent HIV infection.

This adherence objective will be assessed using indirect self-reported measures, including study product counts at the sites' pharmacy, as well as face-to-face interviewing with responses collected via Case Report Forms (CRFs), and Audio-Computer Assisted Self Interviewing (ACASI). It is widely accepted that self-report of study product adherence by participants is inflated^[7]. Similar to self-report, product count estimates are also likely to be inflated if participants forget to return their products or “dump” them (non-returned products can be reported as used by participants). The study design of VOICE also allows limited comparisons of effectiveness, safety, adherence, and associated frequency of viral resistance among HIV seroconverters across formulations. Currently planned biological measures (e.g., drug level in plasma at all VOICE sites; and in Peripheral Blood Mononuclear Cell (PBMC), which is being

considered at some VOICE sites) will only be informative for participants in the VOICE oral group. No biomarkers are currently available for assessing product use in the VOICE vaginal group.

The proposed study, MTN-003-P01 aims to pilot test the feasibility of using Wisebag, a novel event-based electronic monitoring system, as an indirect objective measure of adherence to daily product use. This pilot study will inform the feasibility of including Wisebag in the design of a future VOICE ancillary study on objective measures of adherence.

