2.3 Objective Measures of Product Adherence

Aside from Directly Observed Therapy (DOT), there is presently no validated objective method available to measure participants' adherence to vaginal study product use in HIV prevention trials. Furthermore, DOT is not a logistically practical option in studies of vaginally applied products. Because of the lack of accurate adherence measurement capabilities in HIV prevention (as well as treatment) trials, there has been an indeterminate amount of product non-adherence that may, in turn, preclude researchers' ability to accurately measure the safety or efficacy of a novel vaginally applied intervention technology. The methods commonly used for measuring adherence in HIV prevention (and treatment) research studies include self-report, electronic pill cap monitoring, pill or applicator counts, and application insertion indicators (e.g., mucin test). Each of these methods has strengths and limitations, thereby precluding any of them from serving as a universal "gold standard."

This lack of a gold standard to measure product adherence has challenged the microbicide field, and measurement has typically relied on self-report, which suffers from several biases, including recall and social desirability.^[7, 8] Over-reporting of product use using self-reported measures is notorious, and prevents accurate estimation of the effectiveness or safety of an intervention.^[3, 4] Findings from prevention trials that have measured adherence using both self-report and more objective measures have highlighted discrepancies by mode of data collection.^[2, 9-12] More objective measures of adherence such as applicator stain tests have been used in some microbicide trials^[9, 10], but they have several limitations: They are assessor dependant, and will not work with all types of applicators.^[8, 12-14]

For their Phase 3 Carraguard trial, the Population Council used an applicator staining technique as a surrogate marker for use of a vaginal microbicide. Preliminary results suggest substantial over-report of product use by self-report compared with the applicator staining technique.^[6] The test involves spraying a dye on all used applicators and then rinsing. If mucin is present, the dye "sticks" and is visible as a color changes. As mentioned above, these applicator assays are also time-consuming to process and difficult to reproduce on various applicator types.^[13, 14]

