2.6 Study Hypotheses and Rationale for Study Design

2.6.1 Study Hypothesis

This is primarily an exploratory descriptive study that is not designed to test a hypothesis. However, the objectives of the study are based on the assumption that the “active” Wisebags will successfully and accurately record opening events, and will be acceptable for use by women in the study, and that women will not be able to distinguish between an active and dummy Wisebag.

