2.6.2 Rationale for Study Design

The proposed Wisebag pilot study is a critical step to informing the development of a larger ancillary study for VOICE to objectively measure study product adherence. It is widely accepted that self-reporting of adherence yields inaccurate results, most often inflation, of product use. Adherence, however, is one of the most important components of testing whether or not a study product is effective. Wisebag, an opening event-monitoring bag, is a promising technology that could provide objective measures of the days and times that women may retrieve gel applicators for use. However, the functionality of Wisebag when used daily and in “offline” mode has never been tested, and requires piloting prior to larger-scale deployment in VOICE.

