3 OBJECTIVES

3.1 Primary Objectives

- To compare the on-site technical performance of the “offline” and “online” functionalities of Wisebag
- To assess the success of attempted blinding of the “dummy” vs. active (“online” or “offline”) Wisebag
- To measure the concordance between Wisebag opening-event data (both “online” and “offline”) and self-reported data.
- To explore the feasibility and acceptability of Wisebag use by participants

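### Section 10.2 names as accuracy what is only concordance with a self-report diary, and the planned totals comparison ignores the heart beat, so dead-device loss looks the same as over-reporting

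*Protocol*

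**What the plan says.** Protocol Section 10.2 gives the third main outcome as "signal accuracy of the events monitoring in the online modality versus the offline modality as compared to the diaries provided by participants". Section 3.1 states the matching objective differently: "To measure the concordance between Wisebag opening-event data" and self-reported data, with neither source named as the reference. Section 4.2 also uses the concordance label and classes the diary card as self-reported.

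On self-report, Section 2.2 says: "It is widely accepted that self-report of study product adherence by participants is inflated". Section 2.6.2 says: "It is widely accepted that self-reporting of adherence yields inaccurate results, most often inflation, of product use". Section 2.3 adds: "This lack of a gold standard to measure product adherence has challenged the microbicide field".

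On the device, Section 2.4 says that it "counts and records any opening events, as well as a daily control signal", the heart beat, which shows that the battery is working, and that each opening carries a date and time. Section 4.1 has the woman put each sticker on the card under its day.

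The concordance analysis in Section 10.5.2 covers the active-device groups. It reports the share of women whose signal count is equal to, above or below their diary count, with no formal test. Battery, signal and download failures are counted under the separate performance endpoint in the same section.

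**The concern.** Accuracy needs a reference that is closer to the truth than the thing being tested. By the protocol's own account the diary is not such a reference, so Section 10.2 promises something that Sections 3.1 and 4.2 do not, and that the design cannot deliver from diaries.

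The planned statistic adds a second problem. A woman whose device was dead on some days and a woman who placed stickers without opening the bag on those days both end up with a signal total below the diary total. Section 2.3 reports that electronic monitors gave lower adherence than self-report in earlier work, so this is the result to expect. It can be read as a bag that exposes over-reporting or as a bag that misses openings, and these point in opposite directions for the wider use in VOICE that the pilot is meant to inform (Section 2.4). The working assumption in Section 2.6.1 that the active "Wisebags will successfully and accurately record opening events" would be left untested by this comparison.

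**Working it through.** The plan gives no figure for this endpoint, so there is none to reproduce. The allocation is consistent: 50 split 1:2:2 is 10, 20 and 20, as in Table 3.

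**A simple case.** Take 14 days.
- The bag dies after Day 7 and the diary is honest: 7 signals, 14 stickers.
- The bag works throughout and half the stickers are false: 7 signals, 14 stickers.

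Section 10.5.2 puts both women in the same class.

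**General case.** Inputs:
- D = 14 days (Section 4.6).
- Probability of a sticker on a given day = 0.8 (assumption).
- q = 2% to 20% (assumption). It is either the share of days with a dead device (mechanism A, honest diary) or the share of stickers placed without an opening that day (mechanism B, perfect device).
- Days are independent (assumption).

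Under either mechanism a given day falls short with probability 0.8q, and no day produces a surplus. The signal total is below the diary total if at least one day falls short:

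P(signal below diary) = 1 − (1 − 0.8q)^14

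| q | Calculation | A or B | Simulated A | Simulated B |
|---|---|---|---|---|
| 2% | 1 − 0.984^14 | 20.2% | 20.3% | 20.2% |
| 5% | 1 − 0.960^14 | 43.5% | 43.6% | 43.2% |
| 10% | 1 − 0.920^14 | 68.9% | 68.8% | 69.1% |
| 20% | 1 − 0.840^14 | 91.3% | 91.3% | 91.2% |

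The simulations used 200,000 women per row. If dead days or false stickers come in runs, the percentages change, but a run of one still gives the same totals as an equal run of the other.

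**Totals can also cancel.** A woman with one false sticker on one day and one extra opening on another is classed as equal, although neither day agrees.

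**After a day-level comparison on heart-beat days.** Under A, every remaining day agrees: 100% concordance, with the lost days reported separately. Under B, nothing is removed, so the same 20.2%, 43.5%, 68.9% and 91.3% of women have at least one live day with a sticker and no opening. The two mechanisms now give different results. In the simple case, 7 of 7 live days agree for the first woman and 7 of 14 for the second.

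**What the heart beat does not resolve.** Let m be the chance that a live device misses an opening and f the chance that a sticker is false. The chance that a live-day sticker has a matching signal is (1 − m)(1 − f). With m = 10% and f = 0 this is 0.90; with m = 0 and f = 10% it is also 0.90. Only the product can be estimated.

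**Practice openings.** Table 1 in Section 7.1 schedules: "Practice opening/closing the bag and placing a study sticker on their diary card". The number per woman is not stated. If every one in a 20-woman arm were found in the device record, the exact two-sided 95% lower bound would be 0.025^(1/n), ignoring clustering:
- one per woman, n = 20: 83.2%
- two per woman, n = 40: 91.2%
- three per woman, n = 60: 94.0%

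**The case against.** A reader might infer that this study cannot tell device error from over-reporting at all. The documents do not support that. The heart beat, the time stamps and the day-specific diary would separate dead-device days, and failures are counted under the performance endpoint, so a bag that dies at Day 7 should be visible to anyone who reads both endpoints. The loss is in the concordance statistic alone.

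A reader might also infer that the protocol calls this diary inflated, or that a perfect device would be scored as inaccurate. Neither is quite so. The inflation statements concern self-reported product use in general. Here the stickers are kept in the bag, so each needs some opening, though several could be removed at once. The three-way summary in Section 10.5.2 is symmetric and treats neither source as truth. The reference-standard problem rests on the wording of Section 10.2.

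Randomisation should balance over-reporting between the active arms. That helps only with loss that differs by arm. With 10% false stickers in both arms and 5%, 10% or 20% dead days in the offline arm only, the shortfall class would hold 69% online against 82%, 90% or 97% offline, from 1 − (1 − 0.8[1 − 0.9(1 − dead share)])^14. Loss common to both arms stays hidden.

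Section 2.5 plans a controlled pretest. It names the offline mode and uses the research team, so it does not show performance in participants' hands.

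Finally, heart-beat rules could sit in an analysis plan that is not shown, and the study is descriptive. That limits the weight of the point. It does not remove it: Section 10.2 contradicts Sections 3.1 and 4.2, and Section 10.5.2 names a totals comparison when a better one is available from data already collected. A descriptive result must still be interpretable.

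**Conclusion.** The point holds in a limited form. Section 10.2 should not call the outcome accuracy. The planned concordance statistic cannot attribute a shortfall to device or participant: equal rates of dead-device days and false stickers give the same result, from about 20% of women at a 2% rate to about 91% at 20%. These percentages rest on the assumed 80% sticker rate and independent days; the equality between the two mechanisms does not depend on the 80%. The separation after the change assumes that a heart beat on record marks a day on which the device was able to record.

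It would go too far to expect the practice openings to settle accuracy. They occur only at enrolment, since the exit visit in Table 2 has none, and they take place in clinic on Day 0. They say nothing about home use or two weeks of battery life. The point affects interpretation of one descriptive primary endpoint, not sample size or safety.

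**What to change.** 1. In Section 10.2, replace signal accuracy with concordance, to match Sections 3.1 and 4.2.
2. In Section 10.5.2, add a day-level comparison of time-stamped openings with diary stickers, by modality, on days with a heart beat on record. Report days without a heart beat separately as device failures. Keep the all-days totals as a supplementary summary. State that an opening missed on a live day remains confounded with over-reporting.
3. Optionally, record on the case report form the clock time of each practice opening already done at enrolment, in all three arms so that the blind is kept. Report the share found in the device record by modality, as an in-clinic Day 0 check only. With one opening per woman, 20 of 20 gives a lower bound of about 83%.

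The cost is a few lines in two sections, a little more analysis work, slightly fewer days in the main concordance summary and, if item 3 is taken up, one form line and a little staff time at enrolment.
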